| Secondary Endpoints | 
• Safety characterized by type, incidence, severity, timing, seriousness and relationship to study treatment of adverse events and laboratory abnormalities.• Secondary efficacy endpoints:
○ Duration of Response (DR);○ Progression-Free Survival (PFS);○ 1-Year Survival Rate; and○ Overall Survival (OS).• Gene alterations in tumor tissue and ctDNA at prescreening/baseline.• Change in ctDNA through time.• Blood plasma MGCD265 concentration.• Blood plasma concentration of selected soluble biomarkers. |

Study Design: Study 265-109 is an open-label, parallel arm, Phase 2 trial evaluating the efficacy of MGCD265 in patients with locally advanced, unresectable or metastatic NSCLC exhibiting activating genetic alterations of *MET*.

To be eligible for enrollment, patients must have documented evidence of a genetic alteration activating *MET* as determined by a Sponsor-approved central or local laboratory.

The primary objective of the study is to determine the tumor response to MGCD265 as measured by ORR in accordance with RECIST 1.1. Secondary objectives include evaluation of safety, secondary efficacy endpoints, genetic alterations in tumor tissue and ctDNA at pre-screening/baseline, change in ctDNA through time, and population PK/PD. The Schedule of Assessments to be performed in the study is presented in Table 1, Table 2, and Table 3.

MGCD265 will be administered as an oral therapeutic twice daily (BID) in 21-day cycles. Guidelines for study drug administration and dose reduction in the event of toxicity are provided in the protocol. Study treatment will continue until disease progression, unacceptable adverse events, patient refusal or death.

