Tumor Tissue Genotyping for MET Gene Alteration	Testing Samples from the most recent biopsy or excision are preferred; however if no recently obtained materials are available, samples from any time during patient’s prior disease course are accepted. If study enrollment is based on Sponsor-approved local laboratory results, a tumor tissue sample for confirmatory testing by the central laboratory is expected to be available.
Circulating Tumor DNA Genotyping for MET Gene Alteration	Samples consisting of two 10 mL tubes of whole blood are collected in Streck brand Cell-Free DNA Blood Collection tubes allowing shipping and stability at ambient temperatures.
Evaluation of overall health status for future clinical trial participation	Study eligibility requires adequate performance status and organ function. Patients undertaking pre-screening for tumor /genotype with the goal of considering Study 265-109 should have health status consistent with meeting eligibility criteria in the future when they may become a candidate for the study.

Table 2: Schedule of Assessments – During Study

The Schedule of Assessments provides an overview of the protocol visits and procedures. Refer to Section 7 for detailed information on each assessment. Additional, unplanned assessments should be performed as clinically indicated, including for the purpose of fully evaluating adverse events.

Assessments	Screen/ Baseline	Cycle 1		Cycle 2		≥ Cycle 3	End of Treatment ¹⁴	
	Within 28 days	Day 1	Day 15 (± 2 days)	Day 1 (± 2 days)	Day 15 (± 2 days)	Day 1 (± 2 days)	End of Treatment/ Withdrawal	Post Treatment Follow Up
Study Participation Informed Consent ¹	Before study specific assessments							
Tumor Tissue for Genotyping ²	X							
Medical History, Disease History, Prior Therapy	X							
ECOG Performance Status	X							
Physical Exam ³	X						X	
Abbreviated Physical Exam ³		X	X	X	X	X		
Vital Signs ⁴	X	X	X	X	X	X	X	
Pregnancy Test ⁵	X	As clinically indicated						
Hematology ^{6,7}	X	X	X	X	X	X	X	
Coagulation ^{6,7}	X	As clinically indicated						
Serum Chemistry ^{6,7}	X	X	X	X	X	X	X	
PK Sampling ⁸		X	X	X	X			
PD Sampling ⁹		X	X	X	X			
ctDNA ¹⁰	X			At assessment for confirmation of disease response (PR or CR)			X	
12-Lead ECG ¹¹	X	X	X	X			X	
Disease Evaluation ¹²	X	Q 6 weeks until Week 49 (~1 year) and then Q 12 weeks						
Study Treatment Dispensing and/or Reconciliation		X		X		X		
Adverse Events ¹³ and Concomitant Medications	SAEs only	Throughout						

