12. Disease Evaluations: To be performed at screening (28-day window allowed) and every 6 weeks from dosing date [Cycle 1, Day 1] (-7/+10 days window allowed for first on-study assessment, ± 10 days window for all other assessments) until Week 49 (~1 year) and then every 12 weeks. All on-study disease assessments should be based on a calendar schedule beginning from the first day of dosing. In general, assessments at screening/baseline as well as on-study are to include Computed Tomography (CT) scan with contrast or Magnetic Resonance Imaging (MRI) of the chest abdomen and pelvis. In addition, at screening/baseline, a MRI with and without gadolinium or CT with contrast of the brain, a whole-body bone scan and evaluation of any superficial lesions will be performed. Subsequent disease assessments should also include whole body bone scans and/or MRI of the brain if metastatic disease is identified at screening/baseline by either the **investigator OR the central radiology reviewer**. Bone scans may be performed at one-half the frequency of other radiology evaluations (every 12 weeks) and should be performed during assessment for confirmation of disease response. All scans will be sent to the central radiology reviewer. More detailed guidance on exceptional circumstances is provided in the protocol (Section 7.3).

- 13 Adverse Events: SAEs are to be reported from the time of informed consent for study participation (i.e., excluding prescreening informed consent) until resolution of all SAEs observed on study (SAEs occurring during the screening period are only reported to the safety vendor). Adverse events will be reported from the first day of study treatment until at least 28 days after last dose of study drug, and until resolution or stabilization of acute AEs and/or ongoing SAEs. Post-treatment 28-day follow-up and beyond may be performed by remote contact (e.g., telephone call).
- 14 End of Treatment: Assessments that have been completed in the previous 3 weeks do not need to be repeated (6 or 12 weeks for tumor assessments in accordance with schedule).
- 15 Long Term Follow-up: Survival status and subsequent therapies will be collected by telephone contact every 2 months (± 14 days) from end of treatment visit until death or lost to follow-up.

Table 3: Schedule of PK, Triplicate ECG, and PD Assessments

	Cycle 1, Days 1 and 15 (± 2 days Day 15 only)			Cycle 2, Days 1 or 15 (± 2 days)		

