6.3 End of Treatment Assessment

All patients will be followed for adverse events and serious adverse events for at least 28 days following the last dose of MGCD265. See the Schedule of Assessments (Table 2) for evaluations to be performed at the End of Treatment visit.

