7.4.3 Laboratory Safety Assessments

Laboratory safety assessments for which data will be collected in this study will include hematology, coagulation, and chemistry parameters presented in Table 9.

Laboratory tests will be drawn at the time points described in the Schedule of Assessment table and analyzed at local laboratories. Additional laboratory tests may be performed per standard of care, at the investigator's discretion for the purpose of planning treatment administration, dose modification, following adverse events, or as clinically indicated.

Table 9: Laboratory Safety Parameters

Hematology Panel	Blood Chemistry Panel
Hemoglobin	Aspartate aminotransferase (AST)
Platelet count	Alanine aminotransferase (ALT)
White blood cell count (WBC)	Alkaline phosphatase
Neutrophil count	Total bilirubin
Lymphocyte count	Creatinine
Eosinophil count	Uric acid
Basophil count	Albumin
Monocyte count	Sodium
	Potassium
Coagulation	Chloride
International normalized ration (INR)	Total calcium
Partial thromboplastin time (PTT)	Phosphate
	Magnesium

Pregnancy Testing: For patients of childbearing potential, a serum or urine pregnancy test will be performed at screening. Pregnancy tests will also be done whenever pregnancy is suspected during the study. Additional pregnancy testing may be necessary if required by local practices or regulations.

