9.5.3 Clinical and Laboratory Assessments

Clinical and laboratory assessments include clinical laboratory tests (hematology, coagulation, and chemistry), vital signs, and 12-lead ECGs.

Clinical laboratory results will be listed by patient and, as appropriate, summarized descriptively, which will include a display of change from baseline. Selected parameters will be presented in shift tables of baseline against worst grade test result. Laboratory values outside of the normal ranges will be identified. Laboratory values that meet Grade 3 or 4 criteria according to NCI CTCAE v.4.03 will be listed and summarized.

ECG assessments will be evaluated for change of QTc from baseline as an exposure: response analysis. The investigator's interpretation of QTc will be used in the clinical management of patients. The study analysis will use Fridericia's formula applied programmatically to the ECG data collected in CRFs.

Vital signs and ECG measurements will be listed for each patient at each visit. Descriptive statistics of observed values and changes from baseline will be summarized by treatment group.

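### Table 2 footnote 14 lets a laboratory panel up to 21 days old replace the End of Treatment panel, the visit's timing is undefined, and no later panel is scheduled

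*Combined protocol and SAP*

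**What the plan says.** Treatment runs in 21-day cycles (Study Summary and Section 3: "MGCD265 will be administered as an oral therapeutic twice daily (BID) in 21-day cycles"). Table 2 places hematology and chemistry at screening, on Days 1 and 15 of Cycles 1 and 2, on Day 1 of every cycle from Cycle 3, and at End of Treatment. Visits after Cycle 1 Day 1 carry a window of 2 days either way. Neither test is marked in the post-treatment follow-up column.

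Footnote 14 to Table 2 then relaxes the End of Treatment column: "Assessments that have been completed in the previous 3 weeks do not need to be repeated". It gives tumor assessments their own rule of 6 or 12 weeks. It makes no separate provision for safety laboratory tests, does not refer to the last dose, and does not mention the reason for stopping.

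Section 6.3 gives no timing for the visit; it says "See the Schedule of Assessments (Table 2) for evaluations to be performed at the End of Treatment visit", and Table 2 gives no day or window for that column. Footnote 13 allows the 28-day safety contact to be made remotely.

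Two provisions work the other way. The introduction to Table 2 says "Additional, unplanned assessments should be performed as clinically indicated, including for the purpose of fully evaluating adverse events", and Section 7.4.3 says "Additional laboratory tests may be performed per standard of care, at the investigator's discretion". Section 9.5.3 states how the data are used: "Selected parameters will be presented in shift tables of baseline against worst grade test result", with Grade 3 and 4 values also listed and summarized.

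**The concern.** An End of Treatment panel is normally the one scheduled look at the laboratory values that reflect the final stretch of exposure. Here the waiver reaches back as far as the interval between routine panels, so the routine Day 1 panel of the last cycle can stand in for it. That panel may predate up to three weeks of dosing.

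If the waiver is used, no scheduled value shows what happened in those last weeks, or whether a change recovered or developed after dosing stopped. This matters for this drug because Section 1.2.3 reports related AST and ALT increases in 25% and 20% of patients on single-agent treatment, and such changes can occur without symptoms. It also matters because the protocol provides for expanded enrollment partly to enlarge the safety database for an accelerated approval application.

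**Working it through.** **Inputs.** Waiver window: 3 × 7 = 21 days (footnote 14). Cycle length: 21 days. Scheduled panels on study Days 1, 15, 22, 36, 43 and every 21 days after that (Table 2). The intervals are therefore 14 and 7 days in Cycles 1 and 2, and 21 days from Cycle 3. The lag from last dose to the End of Treatment visit is not in the documents, so it is treated as an assumption and varied from 0 to 28 days.

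**Step 1: share of patients whose panel can be waived.** Let *g* be the days from the last scheduled on-treatment panel to the last dose, and *L* the lag from last dose to the visit. The panel can be waived if *g* + *L* ≤ 21. From Cycle 3, with stops spread evenly, *g* takes the values 0 to 20 with equal weight. The share is then min(21, 22 − *L*)/21, or 0 once *L* exceeds 21. In Cycles 1 and 2, *g* runs from 0 to 13 and from 0 to 6 within each cycle.

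| Lag *L* (days) | Cycle 3 onward | Cycles 1–2 |
|---|---|---|
| 0 | 21/21 = 100% | 100% |
| 3 | 19/21 = 90% | 100% |
| 7 | 15/21 = 71% | 100% |
| 10 | 12/21 = 57% | 19/21 = 90% |
| 14 | 8/21 = 38% | 15/21 = 71% |
| 21 | 1/21 = 5% | 2/21 = 10% |
| 28 | 0% | 0% |

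Adding the 2-day visit windows by simulation (200,000 draws, Cycle 3 onward) gives 98% at lag 0, 72% at 7 days, 38% at 14 and 5% at 21. The windows hardly change the picture.

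**Step 2: length of the gap when the visit falls on the last-dose day.**
- Cycle 3 onward, mean: 21/2 = 10.5 days in continuous time, or (0 + 1 + … + 20)/21 = 10.0 in whole days.
- Cycle 2, mean: (14²/2 + 7²/2)/21 = 122.5/21 = 5.8 days in continuous time, or (91 + 21)/21 = 5.3 in whole days.
- Maximum: 21 days. With windows, two consecutive Day 1 panels can be 17 to 25 days apart, but a panel more than 21 days before the visit is outside the waiver and must be repeated.
- With a lag *L*, a panel accepted under the waiver precedes the last dose by at most 21 − *L* days.

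**Step 3: ECG.** On-treatment ECGs are scheduled only in Cycles 1 and 2. The Cycle 2 set falls on study Day 22, or on Day 36 if taken on Day 15 as Table 3 allows. The latest End of Treatment visit it could cover is Day 22 + 21 = 43, or Day 36 + 21 = 57, give or take the window. The ECG point is thus confined to stops in the first two cycles and part of the third.

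**Step 4: effect on the summaries.** A worst grade is a maximum over the values available. Leaving out a value can only keep that maximum the same or lower it. The direction is therefore fixed, but the documents give nothing from which to estimate the size.

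**The case against.** The strongest reply is that the waiver permits an omission but does not direct one, and that the patients of most concern are tested anyway. A reader might infer that patients stopping for toxicity leave without laboratory follow-up. The documents do not support that. The introduction to Table 2 asks for unplanned assessments to evaluate adverse events. Section 7.4.3 allows further tests to follow them. Section 8.2.1 requires prompt follow-up of Hy's Law findings. Section 5.2.2 with Tables 7 and 8 holds drug until recovery to a stated grade, which for a laboratory toxicity cannot be judged without repeat tests. Section 9.5.3 does not exclude unscheduled values, so these results can enter the worst-grade tables. This part of the reply stands. It does not reach the silent change: those tests depend on a clinical reason, the investigator's judgment or an abnormal result already in hand.

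A reader might also infer that nearly every patient's panel can be skipped. That holds from Cycle 3 only if the visit falls within about 3 days of the last dose, and the protocol does not say when it falls.

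Two further inferences fail on arithmetic. The 2-day window does not stretch the maximum gap to 23 days, because the waiver lapses after 21. Nor can a patient who completes two cycles have a 14-day gap in 42 days: the last panel is on Day 36, about 6 days before Day 42. A gap near 14 days needs a stop just before a Day 15 visit.

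Finally, the primary endpoint, objective response rate, is unaffected. That is correct and limits the weight of the point.

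**Conclusion.** The point holds as a gap in the scheduled safety data. Footnote 14 and the undefined End of Treatment timing together mean that a laboratory panel at or after the last dose is not assured. The waivable share from Cycle 3 runs from about 100% at a 0-day lag to 5% at 21 days and none at 28. With the visit on the last-dose day, the mean gap is about 10 days from Cycle 3 and about 6 days in Cycle 2, with a maximum of 21 days. These figures assume stops spread evenly over the cycle, visits on schedule and use of the waiver whenever it is available.

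The consequence is mainly that silent laboratory changes late in treatment can be missed. The observed worst grades and Grade 3 and 4 counts can then only be unchanged or too low, by an amount that cannot be estimated from the documents. This is an inexpensive improvement worth making, not a flaw in the efficacy analysis.

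**What to change.** Make two changes to Table 2 and Section 6.3.

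1. State when the End of Treatment visit takes place relative to the last dose, with a window.
2. Amend footnote 14 so that, for hematology, chemistry and vital signs, and for the ECG where one from Cycle 1 or 2 could otherwise replace it, the waiver applies only to assessments made on or after the date of the last dose. Keep the 3-week waiver for the other items and the existing 6- or 12-week rule for scans.

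A panel drawn on the day treatment is stopped would still count, so no duplicate is needed in that case. The draw is already in Table 2 and is analyzed by local laboratories, so no new procedure is added. The cost is that some patients have a scheduled sample or measurement taken that could previously be skipped.

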CTCAE	National Cancer Institute Common Terminology Criteria for Adverse Events
ctDNA	Circulating Tumor Cell DNA
DNA	Deoxyribonucleic Acid
DR	Duration of Response
EC	Ethics Committee
ECG	Electrocardiogram
ECOG	Eastern Cooperative Oncology Group
EGFR	Epidermal Growth Factor Receptor
EIU	Exposure In-Utero
FDA	Food and Drug Administration
FFPE	Formalin-Fixed, Paraffin-Embedded
FISH	Fluorescent In Situ Hybridization
GCP	Good Clinical Practice
GLP	Good Laboratory Practice
HDPE	High-Density Polyethylene
HGF	Hepatocyte Growth Factor
IB	Investigator's Brochure

LIST OF ABBREVIATIONS

ICF	Informed Consent Form
ICH	International Conference on Harmonization
IDMC	Internal Data Monitoring Committee
IND	Investigational New Drug
INR	International Normalized Ration
IRB	Institutional Review Board
ITT	Intent-to-Treat
IUD	Intrauterine Device
IV	Intravenous
MedDRA	Medical Dictionary for Regulatory Activities
MET	Mesenchymal-Epithelial Transition Factor
mg	Milligram
mITT	Modified Intent-to-Treat
mL	Milliliter
MRI	Magnetic Resonance Imaging
MTD	Maximum Tolerated Dose
NCI	National Cancer Institute
NE	Not Evaluable
NGS	Next-Generation Sequencing
NSCLC	Non-Small Cell Lung Cancer
ORR	Objective Response Rate
OS	Overall Survival
PD	Objective Progression of Disease
PFS	Progression-Free Survival
PK	Pharmacokinetic
PK/PD	Pharmacokinetic/Pharmacodynamic
PR	Partial Response
PTT	Partial Thromboplastin Time
RECIST	Response Evaluation Criteria in Solid Tumors
RNA	Ribonucleic Acid
ROC	Receiver Operating Characteristic
RTK	Receptor Tyrosine Kinase

LIST OF ABBREVIATIONS

RTPCR	Reverse Transcription Polymerase Chain Reaction
SAE	Serious Adverse Event
SAP	Statistical Analysis Plan
SD	Stable Disease
SDD	Spray-Dried Dispersion
SOC	System Organ Class
$t_{1/2}$	Plasma Half-Life
TCGA	The Cancer Genome Atlas Research
T_{max}	Time to Maximum Observed Concentration
ULN	Upper Limit of Normal
VEGF	Vascular Endothelial Growth Factor
VEGFR	Vascular Endothelial Growth Factor Receptor
WBC	White Blood Cell
WOCBP	Women of Child Bearing Potential

1 INTRODUCTION AND RATIONALE

1.1 Disease and Therapeutic Strategy

1.1.1 Non-Small Cell Lung Cancer

Lung cancer remains the leading cause of cancer-related death in the United States (US). Approximately 221,200 new cases of lung cancer are expected to be diagnosed in the US in 2015, and approximately 158,040 deaths will be attributed to lung cancer (Cancer Facts and Figures-2015). Non-small cell lung cancer (NSCLC) accounts for approximately 83% of lung cancer cases (Cancer Facts and Figures-2015), of which approximately half are classified as adenocarcinoma of the lung; squamous cell carcinoma accounts for approximately one-third of NSCLC cases and large cell carcinoma is less frequently diagnosed.

In 1995, the use of cisplatin-based chemotherapy was reported to lead to modest improvement in survival in patients with advanced NSCLC as compared to best supportive care, with a 27% reduction in death as reported in a meta-analysis of 11 trials (NSCLC Collaborative Group-1995). Subsequently, other chemotherapeutic agents have been reported to be active in NSCLC, leading to a comparison of 4 platinum-based doublets in the first-line treatment setting, all of which demonstrated similar activity (Schiller-2002). The importance of histology in the selection of first-line treatment for NSCLC was later described in the development of bevacizumab and pemetrexed. In a Phase 3 clinical trial, treatment with bevacizumab, a monoclonal antibody directed against vascular endothelial growth factor (VEGF), demonstrated an improvement in survival when added to doublet chemotherapy, specifically in patients with non-squamous NSCLC (Sandler-2006). Similarly, treatment with pemetrexed, an antifolate chemotherapeutic agent, results in an improvement in survival when used as part of a chemotherapy doublet in patients with non-squamous NSCLC, but with a probable decrease in survival among patients with squamous cell NSCLC (Scagliotti-2008). Based on the results of these and other trials, platinum-based chemotherapy doublets, with or without bevacizumab in selected patients, remain a standard of care for most patients with advanced NSCLC in the first-line treatment setting. More recently, a trial of pembrolizumab, a humanized monoclonal antibody directed against PD-1, demonstrated an advantage of pembrolizumab over standard chemotherapy in patients with untreated, advanced NSCLC characterized by $\geq 50\%$ tumor PD-L1 expression. Improvement was reported across multiple efficacy endpoints including survival along with a favorable safety profile (Reck-2016), leading to the approval of pembrolizumab in the first-line treatment setting in this patient population in the US.

Non-clinical and clinical studies have led to increased understanding of the molecular mechanisms underlying the pathogenesis of NSCLC. Abnormalities of genes involving signaling pathways have been described primarily in adenocarcinoma, and have included mutations in *EGFR*, *HER2*, *ROS*, *RON*, *MET*, *KRAS*, and *BRAF*, as well as translocations

such as *EML4-ALK*. In tumors harboring gene mutations in these pathways, the activation of the involved pathway is critical for the survival and maintenance of the malignancy. Such observations have been made in concert with the development and market authorization of several drugs targeting these pathways, including gefitinib (Mok-2009), erlotinib (Shepherd-2005; Rosell-2012), and afatinib (Sequist-2013) inhibiting the EGFR (Epidermal Growth Factor Receptor) pathway; as well as crizotinib (Shaw-2013) and ceritinib (Shaw-2014) inhibiting the ALK pathway. Clinical trials with these targeted agents have demonstrated that patient selection on the basis of tumor genetics can result in high disease response rates in all lines of treatment and have revolutionized the treatment of NSCLC, with targeted agents rapidly becoming standard of care among those patients with sensitizing tumor mutations (NCCN-2016). These observations have led to the paradigm whereby adenocarcinoma of the lung often occurs in the setting aberrant signaling pathways, and the identification and targeting of these pathways lead to significant improvements in outcomes for these patients.

Ongoing studies indicate that aberrations in the MET pathway may be similarly important in identifying patients with NSCLC, particularly those with adenocarcinoma, for targeted therapy. The MET pathway may be dysregulated through many mechanisms in NSCLC, including focal gene amplification, mutations leading to aberrant splicing such that the amino acid sequence correlating to exon 14 is deleted from the protein, or other activating mutations. As a consequence of these abnormalities, the MET pathway is overactive and acts as a tumor driver. Agents targeted to exploit the dependency on the MET pathway may be associated with significant activity, and with the potential for a better safety profile as compared to current treatment options.

